**QuitFast: Evaluating Transcranial Magnetic Stimulation as a
Tool to Reduce Smoking Directly Following a Quit Attempt**

PI: [name].

NCT: NCT03576768

Unique Protocol ID: 00074769

IRB Approval Date: 06/11/2019

Protocol & Statistical Analysis Plan

Protocol.

Overview. We will parametrically evaluate the efficacy of two promising TMS treatment strategies (LTD-like stimulation to the vmPFC (Aim 1), LTP-like stimulation to the dlPFC (Aim 2)) as tools to change smoking behavior and brain reactivity to smoking cues. These aims will be addressed in serial (Aim 1 Years 1-2, Aim 2 Years 3-4). A randomized, double-blind, sham-controlled design will be used for each aim.

In total, 138 smokers will be recruited from the tri-county area surrounding Charleston, SC. Current cigarette smokers seeking to quit smoking and willing to set a quit date will be recruited from the tri-county area (Charleston, Berkeley, Colleton County) using digital and print advertising in diverse media outlets. Following informed consent and screening, participants will be randomized to receive real or sham TMS to the vmPFC (Aim 1, Years 1-2) or the dlPFC (Aim 2, Years 3-4) via a Central Randomization Core (run by the MUSC Data Coordination Unit (see Table 1 and TMS Procedures below for more details regarding sham controls and double blinding procedure).

During the Treatment Phase, participants will receive 10 sequential days of TMS (with additional behavioral and MRI scanning (see Table 1). Participants will be allowed to miss up to 2 TMS visits in a row but all 10 visits must be completed in 14 days.

During the Follow Up Phase, behavioral assessments will be acquired weekly for the first 4 weeks (see Table 1), and daily EMA will be acquired. Additionally weekly EMA assessments will be acquired for 24 weeks (approx. 6 months from quit date).

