Experimental Procedure (Aim 1 and 2): Screening Visit – Consent. Participants will receive a series of assessments designed to evaluate nicotine dependence and use, psychiatric conditions, and mood. These include a standard MUSC clinical intake evaluation screen for research (used in other studies by the PI and Co-I), MINI International Neuropsychiatric Interview (88), TLFB (89), Beck Depression Inventory II (90), State-Trait Anxiety Inventory (91) and Profile of Mood States (92). Data will be collected using REDCap™, and entered directly into the online portal to ensure security and prevent data loss. Study Visit Procedures: At all visits, individuals will provide a urine screen to detect recent use of drugs of abuse and pregnancy, a breath carbon monoxide (CO) sample to detect recent cigarette smoking, and a breath sample to test for recent alcohol use. At visits 1, 6, 10 and follow up visits (Assessment visits), participants will complete a battery of behavioral assessments following active TMS or sham (see Table 2). MRI scanning (at visits 1 and 10) will occur prior to TMS in order to isolate cumulative, rather than acute, effects of TMS. At all visits participants will be required to provide a CO reading at least 50% of their baseline CO measure to ensure they are at least 6 hours deprived from cigarettes. Cigarette deprivation will be used to increase craving and responding for cigarettes. Short term cigarette deprivation has known amplification effects on the brain response to smoking cues (93, 94). Moreover, we have extensive experience with successfully using this deprivation procedure (33, 41).

TMS Procedures. After the MRI scans participants will be escorted into the Brain Stimulation room (30 feet away) where scalp localization will be performed for the TMS procedure. The Cartesian position of the coil (X,Y,Z) will be determined by standardized positions from the EEG 10-20 system: 1) FP1 will be

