used for the left mPFC stimulation (Aim 1), 2) F3 will be used for the left dlPFC stimulation (Aim 2). The angular position of the coil (pitch, yaw, roll) will be determined by the individual's cortical geography beneath FP1 and F3 using the individual's T1 scan for guidance. The locations and coil orientation will be indicated on a nylon cap which will be worn during the TMS sessions. We will then determine the participant's resting motor threshold (RMT, the minimal amount of stimulation required over the hand area of the primary motor cortex to induce contraction of the APB muscle of the hand 50% of the time) via the standardized PEST procedure (106, 107). During each TMS session, we will take a non-identifiable photo of the participants' forehead (eyes covered with an index card) to ensure the coil is correctly placed each time they return to the lab. We will also publish a Standard Operating Procedure document and video file as supplementary material with any publications that arise from this project (as in 111, supplement). Experiment 1/Aim 1: cTBS to the vmPFC. For continuous theta burst stimulation (Aim 1), participants will receive stimulation over the left frontal pole (FP1) (each train: 3 pulse bursts presented at 5Hz, 15 pulses/sec, 600 pulses/train, 60 sec intertrain interval; 110% RMT, MagPro) using a figure 8 coil (Coil Cool-B65 A/P). This protocol has been shown to attenuate the mPFC and striatum in cocaine dependent individuals in the past (63) as well as in nicotine users (see Preliminary Data, Study 4). Experiment 2/Aim2: iTBS to the left dlPFC. For intermittent theta burst stimulation (Aim 2), participants will receive 6 trains of stimulation over the dlPFC (F3) (each train: 3 pulse bursts presented at 5Hz, 15 pulses/sec for 2 sec, 8 sec rest, 600 pulses/train; 110% RMT, MagPro) using a figure 8 coil (Coil Cool-B65 A/P). This is the iTBS sequence initially published (3) which has been used in clinical depression treatment (46). During each real and sham TBS session each day the amplifier output will be escalated ("ramping" in 5% increments over 30 seconds) from 80% to 110% RMT to enhance tolerability. The coil will be left in position during the 60-second intertrain interval. The time between the end of the TBS procedures and the beginning of the behavioral assessments will be compiled and used as covariates in subsequent analyses. ACTIVE SHAM system. The MagVenture MagPro system has an integrated active sham that passes current through two surface electrodes placed on the scalp. The electrodes are placed on the left frontalis muscle under the coil for both the real and sham stimulation sessions. To assess the integrity of the blind (active sham) a questionnaire will be given to both the patients and to the research staff at day 1, 6, 10 to evaluate their opinion on whether they received real or sham, their level of confidence (Likert scale 1-10), and their rationale (text entry).

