Statistical Analysis Plan.

Data analysis plan: Data for this study will be acquired by the members of the [name] lab including graduate students and research specialists. These individuals will also perform data under the guidance of the PI. Manuscript composition will be led by the PI, with the assistance of the research team.

Prior to formal statistical analysis, summary statistics for all variables will be obtained and spaghetti plots will be generated. All behavioral outcome measures will be based on standardized composite scores from the literature. We will also use data reduction techniques (such as factor analysis or principle component analysis) to confirm the applicability of the composite scores in our population. Analyses will be performed for each phase separately.

Behavioral Outcomes: For the treatment phase (10 days of real/sham TBS), the behavioral outcomes include Cigarette demand (Q0 and alpha), Craving (QSU Intention, QSU Relief), and Delay Discounting (\$100 and \$1000). For the treatment phase the analysis will be performed using repeated measures ANOVA on change scores from baseline for each visit. The main independent variable in the ANOVA will be time (visits on day 1, 6, 10), group (real or sham) and their interaction. For correlations of observations across visits an AR(1) structure will be considered and compared with other structures such as compound symmetry and a general structure. The primary hypothesis is the interaction. If the interaction effect for an outcome is significant, we will conclude there is statistical evidence of overall treatment effect. If the spaghetti plots suggest trends (e.g., linear, quadratic, or piecewise changes) we will treat time as a continuous variable and fit repeated measures regression models along with group and its interaction with continuous time as independent variables.

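### The breath CO deprivation check is written as a minimum reading, which is the wrong direction for confirming that participants have not smoked

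*Combined protocol and SAP*

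**What the plan says.** The rule is in the combined protocol and SAP, under Experimental Procedure (Aim 1 and 2), Study Visit Procedures. At all visits a participant must "provide a CO reading at least 50% of their baseline CO measure to ensure they are at least 6 hours deprived from cigarettes".

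Earlier in the same paragraph the protocol says what the measurement is for: every visit includes "a breath carbon monoxide (CO) sample to detect recent cigarette smoking". Straight after the rule it says why deprivation is wanted: "Cigarette deprivation will be used to increase craving and responding for cigarettes", and "Short term cigarette deprivation has known amplification effects on the brain response to smoking cues".

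The measurements that depend on this state are listed in three places:

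- The Overview describes the two stimulation strategies as "tools to change smoking behavior and brain reactivity to smoking cues".
- Study Visit Procedures states that "MRI scanning (at visits 1 and 10) will occur prior to TMS".
- The SAP, under Behavioral Outcomes, lists "Cigarette demand (Q0 and alpha), Craving (QSU Intention, QSU Relief), and Delay Discounting" (at two amounts) for the treatment phase, with visits on days 1, 6 and 10.

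The supplied text nowhere restates the rule as a ceiling or as a reduction from baseline. It does not say under what smoking conditions the baseline CO is taken, or what happens when a participant does not meet the rule.

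**The concern.** The criterion and its purpose point in opposite directions within one sentence. To show that someone has not smoked for some hours, a marker of recent smoking has to be low. The rule requires it to be high enough.

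Deprivation is a measurement condition in this trial. The protocol uses it deliberately to raise craving and responding, and says that it amplifies the brain response to cues. If it varies from visit to visit or from person to person, craving and demand scores and cue reactivity will vary with it for reasons unrelated to stimulation. Nothing else in the supplied text controls it. The one timing covariate, under TMS Procedures, is "The time between the end of the TBS procedures and the beginning of the behavioral assessments will be compiled and used as covariates", which measures time since stimulation and not time since smoking.

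There is also a question of monitoring. Data management, acquisition, and transmission has quality control cover protocol deviations and has two IRBs monitor adherence. Held to the written rule, a properly deprived participant at 25% of baseline is non-compliant and one at 100% is compliant.

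**Working it through.** The plan gives no computed figure to reproduce, so this is a check of direction.

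**Inputs from the documents.** The threshold is 50% of baseline, as a minimum, at all visits. The aim is at least 6 hours without cigarettes. CO serves as a marker of recent smoking, so it falls as time since smoking grows.

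**Step 1: compare the two directions.** Let r = visit CO ÷ baseline CO.

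- As written: pass if r ≥ 0.5.
- Reversed: pass if r ≤ 0.5.

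Both pass only at r = 0.5. For any other r exactly one passes. Readings at 100%, 75% and 51% of baseline pass as written and fail as reversed; 49%, 25% and 10% fail as written and pass as reversed.

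**Step 2: relate r to time since smoking.** Because r falls with time t since the last cigarette, a minimum on r is a maximum on t. Longer abstinence can only move a participant from pass to fail, and more recent smoking only from fail to pass. This holds however baseline was taken, because baseline is a fixed divisor.

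**Step 3: illustrate.** The documents give no CO half-life, so I assume a range of h = 2 to 8 hours. I also assume that baseline reflects usual smoking, so that r = 1 just after a cigarette, and use r = 0.5^(t/h). Then r ≥ 0.5 is the same as t ≤ h.

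| Assumed h (hours) | t = 0 | t = 1 h | t = 6 h | t = 12 h | t = 24 h |
|---|---|---|---|---|---|
| 2 | 1.00 | 0.71 | 0.125 | 0.02 | 0.00 |
| 3 | 1.00 | 0.79 | 0.25 | 0.06 | 0.00 |
| 4 | 1.00 | 0.84 | 0.35 | 0.125 | 0.02 |
| 5 | 1.00 | 0.87 | 0.44 | 0.19 | 0.04 |
| 6 | 1.00 | 0.89 | 0.50 | 0.25 | 0.06 |
| 8 | 1.00 | 0.92 | 0.59 | 0.35 | 0.125 |

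Under the written rule, a participant who smoked within the past hour passes at every assumed half-life, and one abstinent for 12 or 24 hours fails at every one. At 6 hours the participant fails for h = 2 to 5, is exactly on the threshold at h = 6, and passes at h = 8.

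Reversed, the pass region becomes t ≥ h, a minimum time since smoking, which is the kind of condition the purpose calls for. That minimum equals 6 hours only if h = 6. For smaller h the reversed rule admits some people abstinent for less than 6 hours; at h = 8 it turns away someone abstinent for exactly 6 (r = 0.59). So even in the right direction the check supports deprivation but does not prove 6 hours.

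**Step 4: count the measures touched.** The SAP's treatment-phase measures are Q0, alpha, QSU Intention, QSU Relief and delay discounting at $100 and $1000: 2 + 2 + 2 = 6. Craving, which the protocol names as deprivation-sensitive, accounts for 2. Reading responding for cigarettes as including cigarette demand adds 2, giving 4 of 6. MRI cue reactivity is an aim of the trial but is not among these six.

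**The case against.** The strongest reply is that nobody would run the check as worded. The purpose is stated in the same sentence and again in the next, and the protocol says that the team has used this deprivation procedure successfully before, citing two references. A garbled phrase with an obvious meaning may never have affected a reading. That is plausible, and it is why I call this a probable drafting slip. It does not make the text correct: the references are not available here, nothing in the supplied text corrects the wording, and anyone auditing or replicating from this document would apply the check backwards.

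Three further points stand in part:

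- **Baseline is undefined.** If it were taken in a deprived state, 50% of it would not be shown to suit the purpose in either direction. The directional error survives, but the suitability of the 50% level depends on how baseline was taken.
- **Tables 1 and 2 are not in the supplied text.** They could hold another deprivation control, so the statement that this is the only one is limited to the text at hand. CO is also recorded at every visit regardless of the pass rule, so the information on smoking state is not lost, although no analysis of it is stated.
- **Step 1 does not measure an effect.** That opposite inequalities disagree everywhere except at the threshold is true by construction. It shows that the error is complete in direction, not how many readings were misjudged.

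**Conclusion.** The concern holds. As written, the check sets a minimum on a marker of recent smoking while claiming to establish abstinence, and it classifies every reading other than exactly 50% of baseline opposite to a rule in the right direction. Applied literally, it would not standardise deprivation for the craving, cigarette-demand and MRI cue measures.

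The directional conclusion needs only that CO falls with time since smoking, which is how the protocol itself uses CO. The statement that recent smokers pass and sustained abstainers fail also assumes a baseline taken under usual smoking. The half-life range is an assumption for illustration only.

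How many readings were affected cannot be known from the documents, because it depends on whether staff followed the wording or the purpose. I claim no bias in the real-versus-sham comparison: no consequence of failing the check is stated, and the quit date is not placed relative to visits 6 and 10. It should be fixed, because it is an operating threshold applied at every visit and the correction costs almost nothing.

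**What to change.** Amend the sentence so that the criterion matches its purpose: a CO reading of no more than 50% of the participant's baseline, that is, a reduction of at least 50%. The sponsor should confirm that this was the intended meaning.

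In the same amendment, describe the check as consistent with deprivation and drop the claim that it ensures 6 hours, since a halving of CO corresponds to 6 hours only if CO halves in exactly that time, which the documents do not state. It would also help to say under what smoking conditions baseline CO is measured and how a reading that does not meet the criterion is recorded.

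The cost is one phrase for the direction and a few words of clarification, with no added visits, procedures or data. If data have already been collected, the recorded CO readings can show which visits met the corrected criterion.

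### The deprivation check compares every visit with one baseline CO, so once participants cut down a pass no longer verifies 6 hours without cigarettes, and correcting the direction of the 50% rule alone does not cure this

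*Combined protocol and SAP*

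**What the plan says.** The rule is in the protocol under Experimental Procedure, Study Visit Procedures: "At all visits participants will be required to provide a CO reading at least 50% of their baseline CO measure". Its purpose follows in the same sentence: "to ensure they are at least 6 hours deprived from cigarettes". The reason for imposing deprivation comes next: "Cigarette deprivation will be used to increase craving and responding for cigarettes". The same section adds that short deprivation amplifies the brain response to smoking cues. It describes no re-measured CO reference and no criterion based on the time of the last cigarette.

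The Overview describes the population as "Current cigarette smokers seeking to quit smoking and willing to set a quit date" and the treatments as being tested "as tools to change smoking behavior and brain reactivity to smoking cues".

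Outcomes are collected repeatedly under this rule: "At visits 1, 6, 10 and follow up visits (Assessment visits), participants will complete a battery of behavioral assessments". MRI is at visits 1 and 10. In the SAP, "the behavioral outcomes include Cigarette demand (Q0 and alpha), Craving (QSU Intention, QSU Relief), and Delay Discounting". These are analysed as change from baseline with time (days 1, 6 and 10), group and their interaction, and the interaction is the primary hypothesis. Neither CO nor hours since the last cigarette is a named model term. The only timing covariate, under TMS Procedures, is the interval from the end of stimulation to the start of the behavioral assessments.

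**The concern.** A threshold set as a fraction of a single baseline value works only while usual smoking stays near its baseline level. This trial recruits people who intend to stop and tests a treatment meant to change smoking. Once usual CO has fallen, the same reading no longer implies the same time without a cigarette.

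By the protocol's own account, deprivation raises craving and responding for cigarettes and amplifies the cue response, and these are things the trial measures. If the deprivation state drifts between visit 1 and visits 6 and 10, a change score mixes the effect of treatment with a change in measuring conditions. If it drifts differently in the two arms, so does the group-by-time interaction.

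**Working it through.** **Inputs from the documents.** The threshold is 50% of baseline CO at all visits. The intended minimum is 6 h without cigarettes. No CO half-life is given, and the timing and smoking state of the baseline reading are not stated.

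**Assumptions.** CO decays exponentially with half-life h, taken as 3 to 6 h. CO is proportional to recent smoking. Baseline CO was measured in the usual smoking state. Let r be the participant's current undeprived CO as a share of baseline.

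**Ceiling reading (a pass means CO at or below 50% of baseline).** After t hours without smoking, CO is r × 2^(−t/h) of baseline. Setting this equal to 0.5 gives the abstinence that a pass proves:

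t = h × log2(2r), with a minimum of 0.

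*The plan's own equivalence first.* At r = 1, log2(2) = 1, so t = h. Equating 50% of baseline with 6 h therefore requires h = 6 h and unchanged smoking. With h = 3 h, a pass proves 3 h even before anyone cuts down.

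| r | log2(2r) | h = 3 h | h = 6 h |
|---|---|---|---|
| 1.0 | 1.000 | 3.0 h | 6.0 h |
| 0.9 | 0.848 | 2.5 h | 5.1 h |
| 0.75 | 0.585 | 1.8 h | 3.5 h |
| 0.6 | 0.263 | 0.8 h | 1.6 h |
| 0.5 or below | 0 or negative | 0 h | 0 h |

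The last row does not depend on h. Someone whose undeprived CO is already half of baseline passes straight after a cigarette.

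**Floor reading (as printed: a pass means CO at or above 50% of baseline).** Take r = 0.75 and h = 6 h. Immediately after smoking the reading is 75% of baseline, and the participant passes. After 6 h it is 0.75 × 2^(−1) = 37.5%, and the participant fails. Anyone with r below 0.5 fails at every time point, even just after smoking. On this reading the rule works against its stated purpose and fails people who have abstained or cut down.

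**Both readings together.** Turning the rule from a floor into a ceiling removes the contradiction within the sentence but leaves the table above unchanged. If the reference tracked current smoking instead, a pass under the ceiling would prove h hours for every r, so the loss shown in the table comes from the fixed reference.

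**The case against.** The strongest objection is that failing to verify deprivation is different from participants not being deprived. The formula gives the least abstinence that a pass proves, not the abstinence that occurred. A participant who has stopped completely gets 0 h from the formula and may be days abstinent. This stands, and it rules out a tempting stronger reading: that the real arm would pass undeprived, so that its craving and demand would look lower because of the measuring condition, precisely when the treatment works. The documents do not support that direction. Participants who reduce may be less deprived, while those who quit are more deprived and, by the protocol's own logic, might report more craving.

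Nor does this route create a false positive under a full null. If stimulation does not alter smoking, it produces no systematic arm difference in deprivation. Any difference arises after randomisation, through the treatment's effect on smoking, so the issue is interpretation.

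Other limits also stand. The ceiling arithmetic does not apply to the rule as printed. The quit date is not placed relative to the ten sessions, so how far smoking falls by visit 6 or 10 is unknown. A baseline CO taken in an already deprived state would change the hours in the table. Tables 1 and 2 are not in the available text and may already record the time of the last cigarette. CO itself is collected at every visit, so some data for a sensitivity analysis will exist.

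None of this rescues the check. The sentence says it ensures 6 hours, and on neither reading can it do so once smoking has fallen.

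**Conclusion.** The point holds as a weakness of verification. Under the ceiling reading and the stated assumptions, a pass proves 3 to 6 h at unchanged smoking, 1.8 to 3.5 h at three quarters of baseline, and 0 h at half of baseline or below. The last figure needs no half-life, but it does need CO proportional to smoking and a baseline taken in the usual smoking state. Under the printed floor, the rule fails people who have abstained or cut down.

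Deprivation at visits 6, 10 and follow-up is therefore unverified, and it may differ by arm if stimulation changes smoking. Neither the direction of such a difference nor the size of any bias in craving, demand or cue reactivity can be derived from the documents. The case for acting is that the remedy is cheap and the stated check cannot do its stated job.

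**What to change.** 1. Reconcile the wording of the 50% rule with the purpose given in the same sentence, and state when and in what smoking state baseline CO is measured.
2. At every assessment visit (1, 6, 10 and follow-up), record the time of the last cigarette and check it against the protocol's own 6 hours, in addition to CO and not in place of it.
3. Prespecify a sensitivity analysis of craving, demand and cue reactivity that uses hours since the last cigarette and CO. Label it as conditioning on post-randomisation variables: it helps interpretation and does not replace the randomised comparison.

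The cost is one question per visit, a short amendment and a paragraph in the SAP. The downside is partial reliance on self-report, which is why CO stays. A 6-hour minimum does not equalise deprivation between arms, because one arm could average far longer abstinence than the other; recording the hours makes such a difference visible. If Tables 1 and 2 already capture the time of the last cigarette, only the check, the analysis and the clarification in item 1 need adding.

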2. The risks to subjects are reasonable in relation to the anticipated benefits they will gain. Risks to subjects can be satisfactorily minimized to keep the risk to benefit ratio acceptably low. The potential to modulate addiction circuitry has profound scientific as well as health care cost implications.

19) Importance of the knowledge to be gained The proposed research is innovative in several ways. First, we are developing an alternative treatment strategy for nicotine dependence, which involves non-pharmacologic modulation of circuits responsible for the perception of craving. This is a significant conceptual advance for the field of addiction. The knowledge gained from these aims would hasten the pipeline through which TMS could be developed as a *neural circuit, evidence based* treatment option for physicians and providers of treatment for nicotine dependent individuals. Second, while most TMS investigations focus on the relative efficacy of stimulation at a single site (or a single functional network), by evaluating 2 Strategies in this proposal we will be uniquely positioned to advance the field. Through these Aims we will determine if the effects of TMS on nicotine craving are greater when the limbic reward circuit is dampened (Strategy 1, vmPFC) or the executive control circuit is amplified (Strategy 2, dlPFC). Third, we are using a novel stimulation profile, theta burst stimulation (supported by our preliminary data). This stimulation profile will reduce the total time of active stimulation relative to standard 10 Hz rTMS, thus reducing patient burden.

Frequency of DSMB reviews. Annually (every 12 months)

Content of DSM report Number of individuals consented, number of individuals enrolled, gender and race distribution of participants, discussion and listing of all amendments to the proposal, any publications of scientific presentations related to the proposal, review of any AE or SAEs, review of any new scientific literature related to the safety and efficacy of this protocol. 26) DSM Board Plan Meet every 12 months with the PIs (facilitated by videoconferencing) to discuss the information listed in “Content of DSM report”. The content of this meeting will be formalized in a report which will be circulated by email and digitally approved by the PI and DSMB. It will be sent to the MUSC IRB, and to NIDA. The DSMB will be composed of individuals with content-specific expertise in brain stimulation and smoking treatment trials.

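### Any one of six unranked treatment-phase outcomes can establish a treatment effect, with no primary outcome and no multiplicity control: about 11% to 26% false conclusions per aim at an assumed 0.05 per test and correlations from 0.9 down to 0

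*Combined protocol and SAP*

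**What the plan says.** The Behavioral Outcomes paragraph of the SAP states that for the treatment phase "the behavioral outcomes include Cigarette demand (Q0 and alpha), Craving (QSU Intention, QSU Relief), and Delay Discounting", with delay discounting measured at 100 and 1000 dollars. This gives six outcomes in three domains: two demand, two craving and two discounting. They are listed without rank, and the verb leaves room for more, so six is a minimum.

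The model is a repeated measures ANOVA on change from baseline: "The main independent variable in the ANOVA will be time (visits on day 1, 6, 10), group (real or sham) and their interaction". On what counts as the main test the SAP says: "The primary hypothesis is the interaction". The decision rule follows: "If the interaction effect for an outcome is significant, we will conclude there is statistical evidence of overall treatment effect".

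No section names a primary outcome, gives a significance level, or sets out a testing hierarchy, a global test or an adjustment for several outcomes. Factor or principal component analysis is mentioned, but only "to confirm the applicability of the composite scores in our population".

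**The concern.** The rule is written per outcome, and its consequence is a conclusion about treatment. With six outcomes, the plan has six chances per aim to reach that conclusion when TMS does nothing, and nothing limits the total error.

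The purpose is confirmatory. The Overview says "We will parametrically evaluate the efficacy of two promising TMS treatment strategies", each in a randomized, double-blind, sham-controlled comparison. Under the rule as it stands, one chance finding among six supports an efficacy conclusion for a stimulation strategy. Because no outcome is designated in advance, the one that leads the report can also be chosen once the results are visible, and no later analysis can undo that.

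**Working it through.** The document gives no significance level, family-wise error rate or power, so there is no figure of its own to reproduce. The calculation needs few inputs.

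**Inputs**
- Number of outcomes: 6 (SAP, Behavioral Outcomes).
- Test per outcome: group-by-time interaction. It has 2 numerator degrees of freedom with three categorical visits, and 1 if one visit serves as the baseline or time is linear.
- Level per test: not stated; 0.05 is assumed.
- Correlation between outcomes: not stated; a range is shown.

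**Independent outcomes**
- P(at least one false positive) = 1 − (1 − α)^6 = 1 − 0.95^6 = 0.265.
- If the level were 0.01: 1 − 0.99^6 = 0.0585, or 5.9%.

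**Correlated outcomes.** Six null test statistics were simulated (1,000,000 draws) and each was tested at 0.05. A separate simulation of 400,000 draws agreed to within about 0.1 percentage point.

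| Assumed correlation | 1 df | 2 df |
|---|---|---|
| 0.3, all pairs | 24.1% | 24.3% |
| 0.5, all pairs | 20.7% | 21.1% |
| 0.7, all pairs | 16.4% | 16.9% |
| 0.8, all pairs | 13.8% | 14.2% |
| 0.9, all pairs | 10.8% | 11.1% |
| 0.8 within domain, 0.2 between | 21.1% | 21.4% |
| 0.9 within domain, 0.3 between | 18.7% | 19.0% |

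If the two measures in each domain were identical and the domains independent, there would be three effective tests: 1 − 0.95^3 = 0.143. At a common correlation of 0.95 the rate is about 9%, and at 1 it is 5%.

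**After correction**
- Bonferroni at 0.05/6 = 0.00833, which is also Holm's first step: 1 − (1 − 0.00833)^6 = 0.049 with independent outcomes, and at most 5% under any correlation. In simulation Holm across six gave 0.049 or less in every case.
- One named primary outcome at 0.05: 5% for the treatment-effect conclusion.

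**Power cost.** Take a test with 80% power at 0.05. The 80% is illustrative, since the document gives no power calculation for its 138 participants. The figures are for 1 df / 2 df.
- At 0.05/5 = 0.01: 58.9% / 59.3%.
- At 0.05/6 = 0.00833: 56.5% / 56.9%.

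**The case against.** The strongest reply is that an overall effect may mean overall across visits within one outcome, which is a natural reading of a group-by-time ANOVA. Each conclusion then concerns that outcome alone and carries its own 5% error, and whether separately reported claims need family-wise control is debated. Part of this stands: the wording of the claim is weaker on that reading. The chance of at least one false treatment-effect conclusion per aim is nevertheless the same, and the Overview's efficacy purpose limits an exploratory defence.

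The SAP does name a primary hypothesis. That is a term in the model, though, and it is tested once for each outcome, so it does not choose among the six. Nor does the planned factor analysis, which checks existing composite scores and does not reduce six tests to one.

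It is fair to say that every percentage here depends on an assumed level and assumed correlations, and that 11% is not a floor. The rate approaches 5% only as all six tests become effectively the same, which is hard to assume for demand, craving and discounting together. The figures also leave out further flexibility in the SAP: covariance structures are to be compared, and the coding of time may be chosen from the plots.

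Finally, a single primary outcome at 0.05 with five secondaries adjusted separately allows about 1 − 0.95 × 0.99^5 = 9.7% for any nominally significant result, if outcomes are independent. That is correct arithmetic, but it does not undermine the fix, because only the primary outcome may then support a treatment-effect conclusion.

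**Conclusion.** The concern holds, and the rule should be changed before the data are unblinded. As written, it lets any one of at least six unranked outcomes establish a treatment effect, with no primary outcome, stated level or adjustment.

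At an assumed 0.05 per test, the chance of a false conclusion in each aim runs from 26.5% with independent outcomes to about 11% at a common correlation of 0.9. That is at least twice 5% throughout this range. The structural defect does not depend on those assumptions; only its size does.

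**What to change.** Before unblinding, state the significance level as two-sided 0.05 and name one of the six listed outcomes as primary for each aim. The choice is the sponsor's. A QSU craving score is a natural candidate, because the section on the importance of the knowledge to be gained says: "Through these Aims we will determine if the effects of TMS on nicotine craving are greater when the limbic reward circuit is dampened". If so, the SAP should say which QSU score. The choice should also be justified against the Overview, which describes the target as smoking behavior and brain reactivity to cues.

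Replace the decision rule with text such as:

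> A treatment effect will be concluded only if the group-by-time interaction for the named primary outcome is significant at two-sided 0.05. The other five treatment-phase outcomes are secondary and are reported with Holm-adjusted p-values.

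If the sponsor prefers to keep the six outcomes co-equal, apply Holm across all six within each aim. This holds the chance of any false conclusion in an aim at or below 5%.

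The change is to SAP wording and needs no new data. The cost is power for the adjusted outcomes: a test with 80% power at 0.05 has about 59% at Holm's first step among five secondaries, and about 57% at the first step among six. A named primary outcome keeps the full 0.05.
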